2.0 Methodology

2.1 Study design

This is a multi-site, extended case-control study with a preliminary cohort component to assess the evolution of the NPR under selective pressure of antibiotic use and hospital admission for pneumonia in children aged 12-24 months in Malawi. The study will be led by the PhD student, [name], as a PhD fellowship.

NP Resistome Study

Version 5.0 21/05/2025

Page 10 of 30

In the preliminary cohort component, healthy children in the community will have a NPS collected at the first study visit, to determine the baseline community resistome through metagenomic sequencing (see Figure 1).

To assess the impact of oral antibiotics on the NPR, children presenting with pneumonia to community healthcare clinics, Ndirande and Gateway Primary Care Centre (GPCC), will have a NPS collected at the first study visit and 3-months post-recruitment, to determine the antibiotic-exposed resistome through metagenomic sequencing (see Figure 1).

To understand the impact of broad-spectrum intravenous antibiotics and exposure to a hospital environment on the NPR, children hospitalised with pneumonia (without any hospital admission 6 months prior) to Queen Elizabeth Central Hospital (QECH) will have a NPS collected at the first study visit, discharge and 3-months post-recruitment to determine a hospital-acquired resistome through metagenomic sequencing (see Figure 1).

[figure not shown]

Figure 1. Preliminary cohort component of the study. The yellow diamonds represent the key samples groups for NPR comparison.

The case-control component of the study will examine whether a hospital acquired NPR is associated with adverse health outcomes, specifically re-admission to hospital with pneumonia. Children hospitalised to QECH with pneumonia (without admission 6 months prior), who are not re-admitted within 3 months will form the control group (see Figure 2); these participants will have a NPS will be collected at the first study visit (within 24 hours of admission to hospital), discharge from hospital and 3-months post-recruitment to assess for a hospital-acquired resistome. Those hospitalised within the preceding 6 months will be

NP Resistome Study

Version 5.0 21/05/2025

Page 11 of 30

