excluded from this control group, to prevent confounding. Children admitted to QECH with pneumonia within 3 months of a previous hospital admission with pneumonia will form the case group; these participants will have a NPS collected at the first study visit (within 24 hours of admission) only, to assess for a hospital-acquired resistome. Health passport screening and carer-reporting will be used to establish prior hospitalisation.

A 4-week audit of hospital re-admission rates of children aged 12-24 months with pneumonia will be conducted at QECH before starting study recruitment, to further inform sample size calculations.

[figure not shown]

Figure 2. Case-control study design to examine whether a hospital-acquired NPR is associated with re-admission to hospital with pneumonia.

Two flocked NPS will be taken at the first study visit from all study participants; one NPS will be stored for viral PCR analysis (outside this fellowship), the other NPS will undergo metagenomic sequencing. Viral PCR analysis of the NPS will seek to identify RNA pathogens most associated with severe acute respiratory infections requiring hospitalisation in this population: Respiratory Syncytial Virus (RSV) and Influenza A [19]. Only one NPS for metagenomic sequencing will be taken from study participants at subsequent study visits e.g. discharge from hospital and 3-month follow-up. All NPS will be stored at -80°Celsius, following an established protocol [20], prior to DNA extraction using mechanical and chemical lysis to optimise the yield of DNA from low-biomass samples dominated by grampositive organisms. Extracted DNA will undergo metagenomic sequencing. Metagenomic data analysis will be performed using an open-source bioinformatic pipeline that I will develop to determine NPM and NPR composition. A urine sample will also be collected from

NP Resistome Study Version 5.0 21/05/2025

Approved by
College of Medicine

16/06/2025

(COMREC)
Research and Ethics Committee

Page 12 of 30

each participant at the first study visit, and stored for antibiotic assays (outside this fellowship), to assess the impact of antibiotic use prior to seeking healthcare input on NPR composition.

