2.4 Study period

This study will be conducted over a three-year period as a PhD fellowship, with participant recruitment over an 18-month period; see Figure 3. Due to the budget, our study team will not have the capacity to recruit in the community and hospital concurrently; community participants will be recruited prior to hospital participants.

We have chosen a 3-month follow up timepoint, to allow the resistome to return to a post-antibiotic baseline; a previous study demonstrated microbiome recovery within 3 months of infective-asthma exacerbation [23].

Importantly, there is evidence of seasonal variation in composition of the NPM and NPR [24]. Unfortunately, our study team size is restricted by budgetary constraints, therefore we are unable to recruit in the community and hospital simultaneously. We plan to conduct most of the community patient recruitment intensively within a 6-month period, before starting hospital recruitment. To restrict potential confounding due to seasonal effect, we plan to return to the community on an infrequent basis (approximately 3-4 weekly) for healthy community sampling over the following 6 months to ensure a baseline healthy resistome has been sampled across all seasons.

NP Resistome Study

Version 5.0 21/05/2025

Page 14 of 30

	December 2024 - February 2025	March - May 2025	June - August 2025	September - November 2025	December 2025 - February 2026	March - May 2026	June - August 2026	September - November 2026	December 2026 - February 2027	March - May 2027	June - August 2027
Set up study in-country											
Recruitment and data											
collection from COMMUNITY cohort											
Recruitment and data											
collection from											
HOSPITAL cohort DNA extraction and											
sequencing											
Bioinformatic pipeline											
optimisation											
Statistical analysis and thesis preparation											

Figure 3. Study timeline

Samples collected from study participants will be stored for 5 years after the conclusion of the study at Malawi Liverpool Wellcome program. The study will be completed within 18 months of the start of recruitment, or when the recruitment targets have been achieved and all samples collected (if this occurs in a time frame shorter than 18 months). Upon study completion, the Sponsor (LSTM), RECs and MLW will be notified; a report of the study findings will be submitted to COMREC, Blantyre district health office and LSTM.

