2.7.3.6 Exclusion criteria for children hospitalised with pneumonia

- Severe anaemia, with a recorded haemoglobin level < 70 grams per Litre.
- Currently taking long-term antibiotic prophylaxis, TB treatment or immunosuppressive medications.
- Diagnosis of an immunosuppressive illness, including HIV infection.
- Hospital admission within the past six months.

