2.7.3.7 Inclusion criteria for children re-hospitalised with pneumonia

- Child aged between 12-24 months.
- Presence of all of the following symptoms: fever, cough, difficulty in breathing and fast breathing.
- Participant has been prescribed antibiotics for treatment of a lower respiratory tract infection on this presentation.
- Hospital admission to ANY hospital with a lower respiratory tract infection within the past 3 months.

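### Re-admitted cases are swabbed anywhere from 0 to about 3 months after their earlier stay, controls only at the two ends of that interval, and nothing named in the plan matches on or adjusts for time since discharge

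*Protocol*

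**What the plan says.** **Cases.** Section 2.1: "Children admitted to QECH with pneumonia within 3 months of a previous hospital admission with pneumonia will form the case group". On sampling it adds: "these participants will have a NPS collected at the first study visit (within 24 hours of admission) only". The eligibility criterion in 2.7.3.7 is "Hospital admission to ANY hospital with a lower respiratory tract infection within the past 3 months", with no restriction on where in that window the child falls.

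**Controls.** Children hospitalised with pneumonia and not re-admitted within 3 months are swabbed "at the first study visit (within 24 hours of admission to hospital), discharge from hospital and 3-months post-recruitment" (2.1). Their exclusion criterion in 2.7.3.6, "Hospital admission within the past six months", means that the admission swab precedes the hospital exposure under study. Only the discharge and 3-month swabs are post-exposure.

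**Expected course.** Section 2.4: "We have chosen a 3-month follow up timepoint, to allow the resistome to return to a post-antibiotic baseline". The support is a study of microbiome recovery after asthma exacerbation. No rate of loss is given.

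**Analysis.** Section 2.9.1 plans gender matching and unadjusted t-tests, with the pairings in Figure 4. Section 2.9.2 adds conditional logistic regression for re-hospitalisation. The confounders it names are co-morbidities, nutritional status, duration of admission and severity. The list is open-ended, and time since discharge is not on it. The data items listed in 2.1 do not include the date of a case's earlier discharge.

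**The concern.** The third primary objective (1.3.2) asks whether a hospital-acquired resistome persists after discharge and whether it is associated with re-hospitalisation. The hypothesis in 1.2 predicts more abundant resistance genes in re-admitted children. Time since the hospital exposure is a plausible driver of that same quantity, and it differs systematically between the groups. Against the 3-month control swab, cases are on average closer to their exposure, which pushes the result towards the hypothesis. Against the discharge swab, cases are on average further from it, which pushes the result the other way. A reported association, or its absence, could therefore reflect recency and depend on which control swab was used.

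**Working it through.** **1. The plan's own figure.** Section 2.5 uses n = 2(z₀.₉₇₅ + z₀.₉₀)²/Δ² with Δ = 0.505: 2(1.960 + 1.282)²/0.505² = 82.4, so 83 per group. This reproduces. Power at 83 per group is 90.2%. The figure is not in dispute; 83 and 0.505 are used below only as a scale.

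**2. Time since discharge in each group.** Let L be the length of stay, taking 3 months as 90 days.
- Cases: the window runs from the earlier admission, so time since discharge runs from 0 to about 90 - L.
- Controls, discharge swab: 0.
- Controls, late swab: timed from recruitment, which is within 24 hours of admission, so about 90 - L. Assumed stays of 3, 7 and 14 days give days 87, 83 and 76.

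Control swabs therefore sit at the two ends of the case range, with none in its interior.

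**3. Size under no true effect.** Assumptions, none from the documents: the excess E at discharge decays exponentially with half-life h; case swabs are spread evenly over 0 to T days; both groups follow the same course; T = 90. E = 0.505 SD borrows the planning effect size, which section 2.5 derives from one macrolide gene 3.5 years after mass azithromycin. It is not an estimate of a hospital excess.

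With k = ln 2/h:
- mean fraction remaining among cases, m = (1 - e^(-kT))/(kT)
- fraction remaining at the late control swab, r = e^(-kT)
- cases minus 3-month swab = E(m - r)
- cases minus discharge swab = E(m - 1)

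Rejection probability is for a two-sided 5% t-test with 83 per group (noncentral t, 164 df, noncentrality = difference × √(83/2)).

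| h (days) | m | r | vs 3-month, E = 0.505 | rejects | vs discharge, E = 0.505 | rejects |
|---|---|---|---|---|---|---|
| 15 | 0.237 | 0.016 | +0.11 SD | 11% | -0.39 SD | 70% |
| 30 | 0.421 | 0.125 | +0.15 SD | 16% | -0.29 SD | 47% |
| 60 | 0.622 | 0.354 | +0.14 SD | 14% | -0.19 SD | 23% |

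With E = 1.0 SD, the difference against the 3-month swab is +0.22 to +0.30 SD, rejected 29 to 47% of the time.

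**4. Sensitivity.** Allowing for a 7-day stay (T = 83) with E = 0.505 gives +0.12 to +0.15 SD (12 to 16%) and -0.18 to -0.38 SD (21 to 67%). Widening the half-life to 7 to 90 days at the same stay, with a normal approximation, gives +0.06 to +0.15 SD (7 to 16%) and -0.13 to -0.44 SD (14 to 82%). The signs do not change.

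**5. Can two control points correct it?** Only in part. With h = 15, E = 1.0 and T = 90, a straight line between the two control means predicts a case mean of (1 + 0.016)/2 = 0.51, against a true 0.24. The residual bias is -0.27 SD, larger in size than the +0.22 SD it replaces. With h = 60 the line gives 0.68 against 0.62, a residual of about -0.06 SD. The assumed shape of decay therefore matters.

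**The case against.** A reader might infer that time since discharge never overlaps between the groups, or that every case swab precedes every late control swab. The documents do not support that. Both the case window and the late control swab are counted from admission. A case with a 3-day earlier stay who is re-admitted at day 90 is 87 days from discharge, whereas a control with a 14-day stay is swabbed at day 76. What stands is that controls have no swab inside the interval, so most cases cannot be matched on time.

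A reader might also infer that fading by itself is bound to produce a difference. That too goes beyond the text. Persistence is the open question of the third primary objective, and section 2.4 states an expectation about a post-antibiotic baseline, not a rate. The bias is conditional on fading.

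Further points have force. Figures 2 and 4, which I could not see, may name the control swab that is used. That would settle the sign of the bias but not remove it, because both post-exposure swabs sit at an end of the interval and the admission swab precedes the exposure. Section 2.9 is a summary with a detailed analysis plan to follow, and its confounder list is open, so a time term could still be added. That requires the dates. Screening against the 3-month criterion must already establish roughly when the earlier admission was, but the listed data items do not include the discharge date, and no analysis plan can create a mid-interval control swab. Finally, the rejection rates apply to the t-test in 2.9.1, not to the regression in 2.9.2, and at a 0.505 SD excess the bias against the 3-month swab is modest.

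**Conclusion.** The point holds in conditional form. As written, the comparison of cases with controls sets swabs taken throughout a 3-month interval against swabs taken only at its ends, with no named handling of time since discharge. If the resistome fades as section 2.4 expects, cases are biased upward against the 3-month swab and downward against the discharge swab, whether or not the resistome affects re-admission. At a 0.505 SD excess and half-lives of 15 to 60 days, the sizes are +0.11 to +0.15 SD and -0.19 to -0.39 SD. These rest on assumed exponential decay, an assumed excess and an even spread of re-admissions. With no fading there is no bias from this source. The plan should be changed: the third primary objective depends on this comparison, and dates not collected at enrolment would later have to be recovered from records and recall.

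**What to change.** 1. **Record dates.** For every case, record the earlier admission and discharge dates from the health passport already screened for prior hospitalisation. For controls, record the actual number of days from discharge to the 3-month swab.
2. **Model time.** For the third primary objective, replace the unadjusted case-control t-test with a model of the resistome measure on group and time since discharge. It should use the controls' discharge and 3-month swabs, with within-child correlation, and the spread of times among cases. Pre-specify a sensitivity analysis over decay shape, with linear and log-linear forms as a minimum.
3. **Report both comparisons.** Show cases against each control swab, state the expected direction of bias of each, and do not read a difference from one control swab alone as an association with re-admission.
4. **Do not require the case mean to lie outside both control means.** With a 1.0 SD excess and a 30-day half-life, the case mean would have to rise by 1 - 0.421 = 0.58 SD merely to reach the discharge mean, so a true effect of 0.505 SD would be missed.

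**Cost.** A small addition to the case report form and analysis wording, with no extra swabs or participants. Section 2.4 places hospital recruitment after most community recruitment, so the dates may still be added before cases enrol. The downsides are recall error in dates and reliance on an assumed decay shape, because there are only two post-exposure control time points. The adjustment does not remove the separate difference that cases are swabbed during acute pneumonia, whereas controls' post-exposure swabs are taken at discharge or follow-up.

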1.2 Hypothesis

Our hypothesis is that antibiotic use will select for a less diverse group of ARGs, dominated by ARGs that produce phenotypic resistance to the class of antibiotics to which an individual has been exposed; that ARGs will be more abundant in the NPR at discharge from

NP Resistome Study

Version 5.0 21/05/2025

Page 9 of 30

hospital, due to microbiome dominance by the pneumonia pathogen; and that exposure to the hospital environment will drive acquisition of ARGs on MGEs, which could lead to more HGT. Children who are re-admitted to hospital with pneumonia within 3 months of a previous hospitalisation will have a more 'high-risk' NPR than those who remain in the community after hospital discharge, with a greater abundance of ARGs, less diverse NPR and greater prevalence of MGEs.

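### No control swab is in the same state as the case swab, so the case-control contrast alone cannot tie a hospital-acquired resistome to re-admission

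*Protocol*

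**What the plan says.** The case-control component in protocol section 2.1 asks whether a hospital-acquired nasopharyngeal resistome (NPR) is associated with re-admission for pneumonia.

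- **Cases.** Section 2.7.3.7 requires "Hospital admission to ANY hospital with a lower respiratory tract infection within the past 3 months". They are sampled once: "these participants will have a NPS collected at the first study visit (within 24 hours of admission) only, to assess for a hospital-acquired resistome".
- **Controls.** Children hospitalised with pneumonia "who are not re-admitted within 3 months will form the control group". Their swabs are "collected at the first study visit (within 24 hours of admission to hospital), discharge from hospital and 3-months post-recruitment". Children with an admission in the preceding 6 months are "excluded from this control group, to prevent confounding"; section 2.7.3.6 repeats this as an exclusion criterion: "Hospital admission within the past six months".
- **Hypothesis.** Section 1.2 expects re-admitted children to have a higher-risk NPR "than those who remain in the community after hospital discharge", with more resistance genes (ARGs), lower diversity and more mobile genetic elements (MGEs).
- **Analysis.** Section 2.9.1 plans unadjusted t-tests between groups. Section 2.9.2 plans conditional logistic regression, listing co-morbidities, nutritional status, length of admission and pneumonia severity among the confounders.

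The text of 2.1 and 2.9 does not say which control swab is compared with the case swab. Figures 2 and 4 may do so but are not shown.

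**The concern.** A case-control comparison of a measured exposure is interpretable only if the exposure is measured in a comparable state in both groups. Here the case swab is taken at the outcome event, during acute pneumonia, in a child recently discharged from hospital. If acute illness or a recent hospital stay shifts the NPR by itself, cases will differ from controls even when the NPR has no bearing on who is re-admitted.

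At stake is the second half of the third primary objective, the association of a persistent hospital-acquired NPR with re-admission. A positive result could not be read as that association, and a swab taken at the outcome cannot show that the NPR came first.

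**Working it through.** **1. State of each swab, from 2.1, 2.7.3.6 and 2.7.3.7**

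| Swab | Acute pneumonia at presentation | Hospitalised before the swab | Differs from the case swab in |
|---|---|---|---|
| Case, re-admission | yes | yes, within 3 months (100%) | – |
| Control, admission | yes | no admission in 6 months (0%) | prior hospitalisation |
| Control, discharge | no, just treated in hospital | yes, the current stay | treatment stage |
| Control, 3 months | no, scheduled after recovery | yes | acute illness |

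The admission-swab contrast removes acute illness and timing as explanations but coincides exactly with prior hospitalisation. The 3-month contrast does the reverse. There is also a residual difference in elapsed time: controls are swabbed at a fixed 3 months, cases at any point up to 3 months after their earlier admission.

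**2. Can adjustment repair it?** No. Within any one contrast, the illness state or the prior exposure is the same for all cases and the opposite for all controls. It is collinear with case status, so adding it to the conditional logistic model leaves nothing to estimate. The covariates listed in 2.9.2 do not stand in for it.

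**3. The plan's own sample size.** Inputs from 2.5: Δ = 0.505, two-sided 5%, 90% power.

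n = 2(1.960 + 1.282)² / 0.505² = 82.4, rounded up to 83. This reproduces the stated 83 per group; power at 83 is 90.2%.

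**4. Consequence of a state shift.** The documents give no size for the effect of acute illness or prior hospitalisation on the NPR, so d is an assumption, shown over a range. With no true association between NPR and re-admission:

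- SE = √(2/83) = 0.155 SD
- P(reject) = Φ(d/SE − 1.96) + Φ(−d/SE − 1.96)

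| Assumed shift d (SD) | d/SE | P(declared different) |
|---|---|---|
| 0 | 0 | 5% |
| 0.1 | 0.64 | 10% |
| 0.2 | 1.29 | 25% |
| 0.3 | 1.93 | 49% |
| 0.5 | 3.22 | 90% |

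The same table serves for either comparator; only the source of d changes. More participants would raise these rates, because this is bias and not noise.

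**5. What pre-outcome data exist.** The 92 hospitalised children have a discharge swab, and section 2.1 has admissions and mortality recorded at 3 months. Section 2.15.1 cites 18% re-admission over 6 months for severe anaemia. Taking half of that for 3 months (an assumption) gives 92 × 0.09 ≈ 8 events; at 5% to 18% the count is about 5 to 17. With 8 against 84, SE = √(1/8 + 1/84) = 0.37 SD, so a 95% interval of about ±1.96 × 0.37 = ±0.73 SD.

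**6. A possible correction from the community-pneumonia group,** which has first-visit and 3-month swabs: (case − control at 3 months) − (community first visit − community 3-month). With within-child correlation r (assumed), SE = √(2/83 + 2(1 − r)/83):

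- r = 0.5: SE = 0.190, power at 0.505 = 76%
- r = 0.3: SE = 0.202, power at 0.505 = 70%

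**The case against.** The strongest reply is that the protocol claims only association, that sampling at the outcome is ordinary in case-control work, and that the comparator may be named in a figure or in the separate analysis plan promised in 2.9. Naming it there would settle the ambiguity, but not the problem: the sampling times and eligibility rules are fixed in the protocol, and each of the three possible swabs leaves one structural difference. The word association does not help either, since the association found may be with illness state or with having been in hospital.

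Three stronger readings are tempting and are not supported.

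- *Acute illness alone could make the objective positive.* This applies only if the 3-month swab is the comparator. Against the admission swab both groups are acutely ill, and the confounder is prior hospitalisation. The hypothesis wording suggests a post-discharge control swab but does not settle it.
- *Section 1.2 predicts the same signature from acute pneumonia as from re-admission.* It does not quite. The higher ARG abundance "due to microbiome dominance by the pneumonia pathogen" is expected at discharge; lower diversity is attributed to antibiotics; MGE acquisition is attributed to the hospital environment. Against the discharge swab, bias could even run towards the null. The predicted case result could arise in part from state, not that it must.
- *The whole third objective fails.* Persistence is assessed within child from the three swabs of the hospitalised group and is untouched, as are the cohort comparisons among the other groups.

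It is also fair to say that the size of the shift is unknown. At 0.1 to 0.2 SD the false-positive rate is 10% to 25%, well below the upper end of the table.

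**Conclusion.** The concern stands for the re-admission part of the third primary objective. No control swab combines acute pneumonia with a hospital stay in the past 3 months, so a case-control difference can arise wholly or partly from illness state, prior hospitalisation or treatment stage, according to the swab chosen. Neither the unadjusted t-tests nor the regression can remove it. If state alone shifts the NPR by 0.1 to 0.5 SD (assumed), the 5% test at 83 per group rejects 10% to 90% of the time with no true association. That the comparison is confounded follows from the protocol's own rules; only the size rests on assumption. This should be resolved before analysis, because it determines what the study may conclude.

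**What to change.** No new swabs are needed.

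1. In 2.1 and 2.9, name the control swab for each case-control test. Report cases against both the control admission swab and the control 3-month swab, labelling the first as confounded with prior hospitalisation and the second with acute illness.
2. Add an analysis within the hospitalised cohort relating the discharge swab to re-admission or death by 3 months. Here exposure precedes outcome. Report an estimate with a confidence interval, not a decisive test.
3. State that the case-control contrast alone does not show that a hospital-acquired NPR preceded re-admission, or is associated with it independently of illness state and prior hospitalisation.

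The correction in step 6 of the working is at most a sensitivity analysis. Its assumptions must be stated: a similar acute effect in community and hospital pneumonia; a community change that also includes the oral antibiotic course; and possible seasonal differences, since community and hospital recruitment are sequential (2.4). Its power at 0.505 is 70% to 76%. Agreement in sign between analyses should not serve as a decision rule: with about 8 events, the nested estimate takes either sign about half the time under no association.

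The cost is protocol and analysis-plan wording, some analysis time and a more limited conclusion. The nested analysis will be imprecise, with about 8 events among 92 children if the 3-month rate is 9%.
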